11.3 Reporting Procedures for All SAEs/ SADEs/ UADEs

For Non-CE marked device: All SAE/SADE/UADEs need to be reported to the sponsor/legal representative and manufacture **immediately**; regardless of relationship to the device.

For studies of CE marked devices: All incidents need to be reported to the sponsor/legal representative and manufacture **within one working day** of the investigator team becoming aware of them.

Reports of related and unexpected incidents should be submitted to competent authority and ethics committee within reporting timelines summarised below of the Investigator becoming aware of the event, using the applicable report method:

- Serious Public Health Threat Immediately and not later than 2 calendar days
- Death or Unanticipated serious deterioration in state of health Immediately after DHSC established a link between the device and the event and not later than 10 elapsed calendar days following awareness of the event.
- Others Immediately after DHSC established a link between the device and the event and not later than 30 elapsed calendar days following awareness of the event.

12 STATISTICS^{9,10,11}

The plan for the statistical analysis of the study is outlined below. There is not a separate Statistical Analysis Plan document in use for the study.

12.1 Sub-study 1: External validation of algorithms

12.1.1 Calibration:

The model was calibrated using samples with varying viral loads and therefore mostly positive. This approach is reflected in the proposal for retraining the algorithm to take into account new testing devices. By construction, the proportion of positive

"individuals" used to train the model exceeds, in proportion, what we expect to see in a real setting. Therefore, underprediction is unlikely to occur. The model was then used in a real-world setting using the Liverpool pilot data. The positivity rate at the time was low and therefore few positives were observed via LFT and PCR, but given the circumstances, the performance achieved was adequate. The specificity is very likely to be accurate while the sensitivity is likely to be inflated due to the small sample number of positives.

12.1.2 Level of statistical significance:

The aim is 95% sensitivity and 95% specificity within 1% margin. If we see indication of convergence of either of these two values to a value lower than 95%, then we might need to reassess the model calibration. This normally only involves refitting using more data (which could be the pilot data) without changing the structure of the model. We then need to sample more for external validation.

12.1.3 External validation and initial sample size:

Since training and calibration of the algorithm have already taken place, we only need to focus on evaluation and external validation at this point. We will treat specificity and sensitivity separately to ensure accuracy is dealt with accordingly. The focus will be primarily on specificity to ensure an adequate number of positives are observed in the validation process. Ideally a minimum of 100 positives should be observed. However, the expected performance of 95% sensitivity and 95% specificity might be achieved earlier. It is worth noting that a minimum of 100 negatives is also necessary but this will almost certainly be achieved in the first ATS batch.

 It is almost certain that we will have a magnitude larger in terms of negative images due to low prevalence, but we would be looking for a minimum of 2500 negative samples to demonstrate specificity, although this is likely to be larger due to the minimum requirement of positive samples above

- We will review and calculate sensitivity / specificity for each image batch, reestimating the values and our projection as sample sizes increase. If we need to use more than one batch of ATS images, this will allow us to rebuild the ROC curves at each stage to determine our ability to meet the benchmarks set by our primary objectives.
- Any contested results will be reviewed by a third party.

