The initial focus will be on estimating the Receiver Operating Characteristic curve (ROC curve) and the area under the ROC (AUCROC). Since specificity is likely to be high, we will need to aim for a large AUCROC to ensure minimum sensitivity of 95%. We will use bootstrap to assess the variation of the AUCROC and derive confidence intervals for the measure but also for specificity and sensitivity. Once the confidence intervals for these measures are small enough or show signs of convergence, we will reassess the study. If the minimum sensitivity and specificity is achieved, a proposal to go live should be made. If, for large sample sizes (50 positives and 100 negatives as a minimum), sensitivity or specificity start to converge to a lower value than expected, model calibration and validation data quality should be reviewed.

12.1.5 Other monitoring tools:

- a) Brier's score: we will observe and note the Brier score for this model. If we note substantial deviation from what is considered appropriate (0 to 0.25), we will reassess the model for overfitting and try to identify other deviations that could have led to issues with discrimination. This tool will be used for monitoring purposes only.
- b) Cross entropy loss: We will use the log loss approach to monitor the discrepancy between label and predicted probability. We don't expect the model to be perfect (log-loss of 0), but we will use this approach to identify when and if the model is possibly confidently wrong.

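### ROC curves and AUC are used to judge the 95%/95% benchmarks, but they show what some cut-off could achieve, not how the AI read actually returned performs

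*Protocol*

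**What the plan says.** The target is in Protocol Section 12.1.2: "The aim is 95% sensitivity and 95% specificity within 1% margin". Section 12.1.3 opens the relevant item with direct estimation, "We will review and calculate sensitivity / specificity for each image batch". It then says that using more than one batch of test-site images would allow the team to "rebuild the ROC curves at each stage to determine our ability to meet the benchmarks set by our primary objectives".

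Section 12.1.4 gives the ROC curve and its area first place: "The initial focus will be on estimating the Receiver Operating Characteristic curve". It reasons that, because specificity will probably be high, "we will need to aim for a large AUCROC to ensure minimum sensitivity of 95" per cent. Bootstrap is to be applied to the AUC and used to "derive confidence intervals for the measure but also for specificity and sensitivity". The review trigger covers all three: "Once the confidence intervals for these measures are small enough or show signs of convergence, we will reassess the study". The release rule in the same section names only two: "If the minimum sensitivity and specificity is achieved, a proposal to go live should be made".

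Section 3 defines the primary outcome as agreement between the AI read and the human read. Section 4 says that the algorithm returns an interpreted result for each image and that the sensitivity and specificity of the AI read will be measured. Section 12.1.5 shows that a predicted probability also exists, so an ROC curve can be drawn. No section gives the cut-off that turns the probability into a read, or says that it is fixed before validation. Section 12 states that no separate statistical analysis plan is in use.

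**The concern.** A reader of test strips gives one answer per image, so it works at one point on its ROC curve. The curve drawn from the validation images shows all the other points as well. Using it to decide whether the benchmarks can be met answers a different question: whether some cut-off would meet them on these images. The AUC is further removed, since it averages over all cut-offs. A large value does not fix sensitivity at any one of them, and at a given AUC the sensitivity falls as specificity rises. High specificity is the situation that the protocol expects.

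At stake is the evidence that Section 17 says will go to the regulator. With the cut-off not declared fixed, the benchmarks could appear attainable from the curve while the reader in use misses them.

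**Working it through.** **Inputs.** From the protocol: benchmark 95% for each measure with a 1% margin (12.1.2); ideally at least 100 positives, and at least 2,500 negatives (12.1.3). It states no AUC target, cut-off or score distribution, so there is no AUC figure of its own to reproduce. Assumed here: normally distributed scores in positives and negatives, with equal variance unless stated. The cut-offs are examples.

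**1. Does a large AUC secure 95% sensitivity?** With equal variances, d = √2 × z(AUC) and sensitivity = Φ(d − z(specificity)). For AUC 0.99, d = 1.414 × 2.326 = 3.290.

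| Specificity | Calculation | Sensitivity |
|---|---|---|
| 95% | Φ(3.290 − 1.645) | 95.0% |
| 98% | Φ(3.290 − 2.054) | 89.2% |
| 99% | Φ(3.290 − 2.326) | 83.2% |
| 99.9% | Φ(3.290 − 3.090) | 57.9% |

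For 95% sensitivity the AUC would have to be 0.990 at 95% specificity and 0.9975 at 99%. If the standard deviation in positives is 0.5 or 2 times that in negatives, AUC 0.99 gives 70.9% or 92.5% sensitivity at 99% specificity. The AUC alone therefore does not determine sensitivity.

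**2. Can the curve show 95%/95% when no cut-off truly reaches it?** Take true sensitivity and specificity of 94% each: d = 2 × z(0.94) = 2 × 1.555 = 3.110, AUC 0.986. Each look has 100 positives and 2,500 negatives.

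- At the fixed cut-off, both point estimates must reach 95%. P(Bin(100, 0.94) ≥ 95) = 0.441 and P(Bin(2500, 0.94) ≥ 2375) = 0.0176. The product is 0.0077, about 1%. Simulation (4,000 runs) gave 0.75%.
- At any cut-off on the curve, simulation gave 26.5% (4,000 runs), and a repeat with 20,000 runs gave 28.0%. As a check, the cut-off with 95% specificity has true sensitivity Φ(3.110 − 1.645) = 92.8%, and P(Bin(100, 0.928) ≥ 95) is about 27%.

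The gap arises because a free cut-off can be moved until specificity no longer fails. Only the sampling error of 100 positives then stands in the way.

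**3. What does the AUC interval add to the convergence trigger?** Hanley–McNeil with AUC 0.99: Q1 = 0.99/1.01 = 0.9802 and Q2 = 2 × 0.9801/1.99 = 0.9850. The variance is [0.0099 + 99 × (0.9802 − 0.9801) + 2499 × (0.9850 − 0.9801)]/(100 × 2500), which with unrounded Q values is 4.93 × 10⁻⁵. The half-width is 1.96 × 0.00702 = 1.4 points. For sensitivity it is 1.96 × √(0.95 × 0.05/100) = 4.3 points. The ratio is 3.1, and it stays at 3.1 for 50, 200 and 400 positives.

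**The case against.** The strongest reply is that the decisions do not rest on the ROC curve. Sensitivity and specificity are calculated for each batch and given intervals. Sampling stops on those estimates, and the go-live proposal depends on them. Sections 3 and 4 define them on the read that the algorithm returns, which is by construction at the operating cut-off. This stands. A reader might infer that the benchmark counts as met if any point on the curve reaches 95%/95%, or that success is judged by AUC. The protocol says neither.

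The ROC curves are rebuilt only if more than one batch is used, and Section 12.1.4 thinks one batch will probably do. This limits that clause, but not the AUC sentence or the convergence trigger, which apply with one batch too.

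The AUC sentence could be read as a necessary condition: with high specificity, 95% sensitivity does require a large AUC. Step 1 supports that reading, but it is not what the sentence claims.

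Section 12.1.2 already asks for further sampling after a refit. That covers a refitted model, but does not mention a change of cut-off alone.

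Two further readings are tempting and do not hold. The first is that the AUC interval narrows faster than the sensitivity interval. It is about a third as wide, but both shrink at the same rate. The second starts from a reader at 85% sensitivity and 99% specificity, for which some cut-off shows 95%/95% in about 74% of looks, and takes that as optimism from selection. On that curve the true sensitivity at 95% specificity is 95.7%, so a compliant cut-off does exist. The example shows only that the curve describes a different reader from the one in use.

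**Conclusion.** The point holds in a limited form. The protocol assigns ROC curves and the AUC a part in judging the benchmarks, while its endpoint and its stopping and go-live rules concern one fixed read. The claim that a large AUC secures 95% sensitivity is wrong as a statement about the cut-off in use: at AUC 0.99 the sensitivity is 95.0% or 83.2%, depending on whether specificity is 95% or 99%. In the 94%/94% case the curve suggests the benchmarks are attainable in about 27% of looks, against about 1% for the fixed read. Both figures depend on the assumed binormal shape. The second also depends on the chosen true values and on 100 positives and 2,500 negatives. They show how far the curve and the read can diverge, and do not predict this algorithm's results.

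The documents do not show that a cut-off will be chosen from the validation curve. They leave that possible, because no cut-off is declared fixed and no separate analysis plan exists to do so. The change is worth making before the first batch is analysed.

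**What to change.** In Sections 12.1.3 and 12.1.4:

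- State that the operating cut-off is fixed before the first batch of test-site images is analysed.
- State that sensitivity and specificity, with their intervals, are judged against the benchmarks only for the read returned at that cut-off.
- Describe ROC curves and the AUC as descriptive output, and remove their link to meeting the benchmarks.
- Delete the clause saying that a large AUC secures 95% sensitivity.
- Base the convergence trigger on the sensitivity and specificity intervals only.
- Extend the Section 12.1.2 rule on sampling after a refit to any change of cut-off, with performance then estimated only on images received after the change.

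The cost is protocol wording. The reported performance may look slightly less favourable, and a changed cut-off would need new images.

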The initial focus will be on estimating the Receiver Operating Characteristic curve (ROC curve) and the area under the ROC (AUCROC). Since specificity is likely to be high, we will need to aim for a large AUCROC to ensure minimum sensitivity of 95%. We will use bootstrap to assess the variation of the AUCROC and derive confidence intervals for the measure but also for specificity and sensitivity. Once the confidence intervals for these measures are small enough or show signs of convergence, we will reassess the study. If the minimum sensitivity and specificity is achieved, a proposal to go live should be made. If, for large sample sizes (50 positives and 100 negatives as a minimum), sensitivity or specificity start to converge to a lower value than expected, model calibration and validation data quality should be reviewed.

12.1.5 Other monitoring tools:

- a) Brier's score: we will observe and note the Brier score for this model. If we note substantial deviation from what is considered appropriate (0 to 0.25), we will reassess the model for overfitting and try to identify other deviations that could have led to issues with discrimination. This tool will be used for monitoring purposes only.
- b) Cross entropy loss: We will use the log loss approach to monitor the discrepancy between label and predicted probability. We don't expect the model to be perfect (log-loss of 0), but we will use this approach to identify when and if the model is possibly confidently wrong.

12.2 Sub-study 2: Human Usability Study

Sub-study 1 will be used to demonstrate the primary objective in this study and validate the algorithm used for classification. In Sub-study 2, the focus turns to user experience, adoption and adequacy of the service provided.

We will monitor the web service metrics and measure effectiveness and efficiency primarily. We will also use a survey and interviews to assess user satisfaction and identify areas for service improvement.

We will also continue to monitor the algorithm accuracy, investigate contested cases, and monitor the reported values used for classification to ensure changes in performance after the service goes live are identified early. We expect to see a small sample of positives (at least 50 if possible) and negatives (at least 100) to be inspected weekly as well as the contested cases. If a systemic bias is identified, the protocol for retraining should be followed to ensure the algorithm can adequately account for new cases (e.g., new test devices, unforeseen user errors).

Effectiveness: we will observe completion rate and number of errors to assess effectiveness. Completion rate constitutes successful submission of an image by the user and receipt of test interpretation by the algorithm. We will record and report failed attempts at different points of the user journey and identify potential areas for review. We expect completion rate to be at least 95% and to increase with time as users adapt to the service and reviews take place to address any systemic issues.

Efficiency: We will focus on time to completion to measure efficiency and reflect on user feedback (survey and interviews) to assess whether the total journey time is appropriate for the service provided. We will investigate outliers to determine the main barriers affecting completion times.

Satisfaction: We will deploy a survey to capture the overall user experience and followup with interviews to further explore barriers and facilitators in the current service. We will observe the response rate and note the sentiment and level of satisfaction captured but will not use these as a direct measure of satisfaction since we will not be able to adequately control for self-selection and non-response biases. We will, however, use the survey data to potentially identify cohorts and investigate whether they need to be targeted for further feedback to ensure they are being adequately catered for.

12.3 Analysis Population

For Sub-study 1, the target population in the study is representative of the general population and they are sufficient to show accuracy and some level of robustness.

For Sub-study 2, the initial target population will be, in some cases, more skilled than the general population but this bias can be partially corrected by capturing basic demographic information. The regular re-evaluation and monitoring after it goes live is essential to review performance.

12.4 Procedure for Accounting for Missing, Unused, and Spurious Data

Sub-study 1: we will note and report the number of images that don't meet minimum quality requirements and the reason for their removal. Since the ATS staff are not using the same portal as the final user, image quality is likely to be lower than expected. We don't expect any missing data as an output from the algorithm and we will be able to complete the external validation process once enough suitable images are observed.

Sub-study 2: Survey – we will first investigate whether missingness or non-response appears to be random based by first analysing demographic and cohort-based questions. If deemed to be random, we will use multiple imputation where possible. If survey response does not seem to be missing at random and high missingness is present, we will report at first by cohort and use multiple imputation where possible. If possible, we will then identify cohorts for interview before proceeding with imputation or deletion when reporting for the full sample.

We are likely to observe incorrect or spurious values in free text questions. Age and other numerical answers will be imputed by median. We might also observe nonresponse for some demographic-based questions such as gender and ethnicity which we will then impute to "Prefer not to say" or similar. It is worth noting that the survey is being used as a sentiment and user satisfaction tool rather than a tool for estimating specific characteristics in a population so incorporating other tools such as

interviews as part of the analysis process is adequate. Deletion will only be used when imputation proves to not be possible (e.g., most answers missing).

Service-related failures: We don't expect missing data at this stage. There are instead a number of expected errors to be observed and monitored as part of the user journey. The service around the algorithm may return: error 400 - likely to be caused by image corruption and invalid requests, or error 500 – likely to be linked to write issues to database or image store. See Table 1 below. These cases cannot be used for the ongoing assessment of the algorithm's performance per se but need to be monitored as part of service usability. We will also need to assess how different errors are presented to the user and whether they have any impact on their journey.

Status Code	Error Message	Cause			
400	Request type is not Json	Invalid request header			
400	Request body is empty				
400	Request body does not contain image_id	No image_id key present in json			
400	Request body does not contain image_data	No image_data key present in json			
400	Image_id is too short	Image_id should be at least 5 characters			
400	Image_data is empty	Image_data is empty string			
400	Failed to decode image	Cannot parse the image data into matrices			
500	Prediction failed	Could not get results from model 1			
500	Failed to store image	Error with writing image to blob store			
500	Failed to store image	Error with writing to database			

Table 1: Service-related failures coding

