1.6 User checks all answers and reports result

Participants

Participants for the trial will be recruited from two use case groups:

- Adult Social Care
- Primary Care (Community pharmacy, NHS Optometry, NHS Dental and General Practice)

Methodology

A survey will be distributed via comms teams to the use case groups to be completed during the trial period.

This survey will collect data on the participant's themselves and their experience of using the product during the trial, as well as operate as a recruitment tool for qualitative interviews.

Interviews to be conducted with 15 participants from each use case group (Adult Social Care and Primary Care) who consent to be contacted for a follow-up interview. The interview will cover their survey responses in more depth, and to attempt to establish the root cause of any user errors or difficulties encountered.

Adobe analytics will also be used to identify user interactions across the digital journey, including any drop off points.

Survey Questions

User Profile

- Sector of work
- Job Title
- Context of Use
- Gender
- Age
- Ethnicity
- Internet Use
- Accessibility software used
- Disabilities or long-term health conditions

Usability Questions

- How many Covid-19 Lateral Flow tests have you taken so far during the trial? (If you are a nominated person responsible for reporting all staff lateral flow test results, please tell us how many test results you have reported in total)
- Of these, how many times did you take and upload a photo of the lateral flow test strip?
- If you did not take and upload a photo every time, please tell us why
- Did you ever have to try more than once to take and upload a photo?
- How many times did you have to try more than once?
- If you had to try more than once, at any time, please tell us more about what happened
- How easy did you find it to take and upload a photo of the lateral flow test strip?

Interview Script

Welcome and Intro

- Purpose
- Consent and confidentiality
- Recording
- Observers

Recap

Refer back to their survey answers for prompts:

- Can you tell me a little bit about how you found taking and uploading a photo of your test?
- What device did you use?
- Where were you when you were taking the test/taking the photo?
- How did you approach it?
- Did you experience any difficulties doing this?
- Did you need to get any help or assistance from anyone else?

Improvements

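### Section 12.4 gives two unreconciled imputation rules for numerical survey answers, and the median fill would distort the age and self-reported retry summaries

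*Protocol*

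**What the plan says.** Section 12.4 of the Protocol handles missing answers in the Sub-study 2 survey. The judgement on whether non-response is random is "based by first analysing demographic and cohort-based questions". Two branches follow.

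- Random: "If deemed to be random, we will use multiple imputation where possible".
- Not random: "If survey response does not seem to be missing at random and high missingness is present", then "we will report at first by cohort and use multiple imputation where possible". Where feasible, cohorts are chosen for interview before anything is imputed or deleted for the full sample.

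The next paragraph opens with "We are likely to observe incorrect or spurious values in free text questions" and continues with "Age and other numerical answers will be imputed by median". Deletion is reserved for cases where imputation cannot be done.

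The survey items are in Appendix 2. Besides age, the numerical ones are the number of tests taken, the number of photos uploaded, and "How many times did you have to try more than once". Section 12.2 uses the survey to help find cohorts that may need targeted feedback. The opening of Section 12 states that no separate SAP is in use, so Section 12.4 is the operative rule.

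**The concern.** Multiple imputation and a single median fill cannot both be the rule for the same missing answer, and the section gives no order of precedence. An analyst could follow either and be compliant.

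The median rule is the weaker of the two. It puts every missing age at one point, and it replaces every missing count with a value that, for a right-skewed count, lies below the mean. Because deletion is a last resort, reporting the answers as observed is not the default.

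Separately, standard multiple imputation relies on data being missing at random given the variables in the model. Section 12.4 keeps it in the branch where that has been judged not to hold, and names no sensitivity analysis there.

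At stake are the descriptive survey results: the age profile used to look for poorly served cohorts, and the self-reported picture of how often users had to try again.

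**Working it through.** The Protocol gives no survey sample size, missing rate or expected count, so there is no stated figure to reproduce. The figures below show the effect of the rule under assumptions.

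**1. Mean of a count after a median fill.** Let f be the share missing completely at random. Then

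reported mean = (1 − f) × true mean + f × median.

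The shift is f × (median − mean), which is negative whenever the median lies below the mean. Two assumed negative binomial retry counts were used: one with mean 0.60 and median 0, the other with mean 2.0 and median 1.

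| f | True mean 0.60, median 0 | True mean 2.0, median 1 |
|---|---|---|
| 5% | 0.95 × 0.60 = 0.57 | 0.95 × 2.0 + 0.05 = 1.95 |
| 10% | 0.90 × 0.60 = 0.54 | 0.90 × 2.0 + 0.10 = 1.90 |
| 20% | 0.80 × 0.60 = 0.48 | 0.80 × 2.0 + 0.20 = 1.80 |
| 30% | 0.70 × 0.60 = 0.42 | 0.70 × 2.0 + 0.30 = 1.70 |
| 40% | 0.60 × 0.60 = 0.36 | 0.60 × 2.0 + 0.40 = 1.60 |

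A simulation with an assumed 500 respondents and 3,000 runs agrees to within about 0.01. At 20% missing, the observed answers alone return 0.60 and 2.00.

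**2. Missingness that depends on the answer.** Suppose users with at least one retry are three times as likely to leave the item blank, with 20% missing overall. The same simulation gives:

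| True mean | Observed answers only | Median fill |
|---|---|---|
| 0.60 | 0.48 | 0.38 |
| 2.0 | 1.86 | 1.69 |

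Reporting as observed is then also too low, and the median fill is lower still. This is why the not-at-random branch needs best and worst cases and not merely a different fill.

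**3. Spread of age.** If mean and median age are close and ages are missing completely at random, the filled values add almost no variance. The SD then shrinks by a factor of √(1 − f):

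- f = 20%: √0.80 = 0.89, about 11% too small.
- f = 30%: √0.70 = 0.84, about 16% too small.

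The age band containing the median also gains a share f of all respondents, whatever their true ages.

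**4. The not-at-random branch.** The check in Section 12.4 compares response across observed demographic and cohort questions. It can show that missingness is not completely at random. It cannot show whether missingness also depends on the unseen answer. If it depends only on the observed variables, multiple imputation using them may be valid. If it depends on the answer itself, standard multiple imputation is biased. The wording does not separate the two cases.

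**The case against.** **The median sentence may be narrower than it looks.** It follows a sentence on spurious free-text entries and may have been meant only for those. That is possible, but as written it covers all numerical answers.

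**The not-random branch is more careful than a bare imputation rule.** It also requires high missingness and puts cohort reporting, and interviews where feasible, first. If its wording loosely means not completely at random, imputation within cohorts could be sound. This stands as mitigation, but the text still needs to say what is meant.

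**The direction of the bias is not certain.** Skip logic is not shown. If only users who reported a retry see the count question, its median is at least 1. If users with no retry leave it blank and are filled, they gain retries they did not have. The downward shift holds for ordinary item non-response on a right-skewed count.

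**The survey is not inferential.** Section 12.4 calls it a sentiment and satisfaction tool, and Section 12.2 declines to treat it as a direct measure of satisfaction because non-response bias cannot be controlled. This stands and limits the severity.

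Three stronger readings are tempting but unsupported:

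- *The study's error counts would look better.* Appendix 2 counts errors made while taking and uploading the image, and Section 12.2 records failed attempts along the user journey. Neither is said to come from the survey, and Section 12.4 expects no missing data for service failures. The 95% completion and efficiency targets are not survey-based either.
- *Confidence intervals would be too narrow.* A naive interval after a median fill would be, but none is planned for a survey item. The planned intervals concern the ROC area, sensitivity and specificity in Sub-study 1. Properly done multiple imputation does not wrongly narrow intervals by itself.
- *The correction for skilled users would be compromised.* Section 12.3 says that "this bias can be partially corrected by capturing basic demographic information", but specifies no age-weighted estimate and no use of imputed survey age.

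**Conclusion.** The point holds as a minor defect. Section 12.4 contains two unreconciled rules for the same numerical survey answers, and the median rule distorts the summaries it produces. Under the assumed skewed count with 20% missing completely at random, the mean falls from 0.60 to 0.48, a 20% understatement (0.12 / 0.60). The SD of age would be about 11% too small at the same missing rate. Keeping multiple imputation where data are judged not missing at random is a second, smaller flaw, partly offset by the cohort reporting that comes first.

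The sizes rest on assumed missing rates and count distributions, and for age on a mean close to the median. The contradiction itself rests only on the text. No primary result, usability target or planned interval changes.

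**What to change.** In Section 12.4:

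- Delete the median rule and set impossible numerical values to missing.
- Report age and count answers as observed, with the number missing beside each.
- Use multiple imputation only where missingness is plausibly explained by the observed demographic and cohort variables, and say so in place of the present random / not-random wording.
- Otherwise report by cohort without imputation, or with stated best and worst cases. For retries, one such case could count every missing answer as at least one retry.

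The cost is a few sentences of wording and slightly smaller numbers in some survey tables. No data collection changes.
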